APPENDIX 4. RASH MANAGEMENT

For subjects reporting rash, the following should be performed:

All rashes will be discussed between the Investigator and the Sponsor, and in case of a causal relationship between the rash and the study drug, then the following visits and assessments will be performed as indicated below and in the "Visit Schedule for Rash Management" (see Appendix 5). Unscheduled follow-up visits for close follow-up of rash will be performed based on the grade (severity) of the rash. At the Investigator's discretion, additional visits and assessments may be performed.

The rash event should be captured in the AE section of the electronic case report form (eCRF), as well as in more detail in the specific rash assessment pages of the eCRF.

In case of rash, blood samples need to be collected for safety laboratory testing, and processed by the local laboratory. These samples need to be collected during the unscheduled visits as described below and in Appendix 5. A copy of the local laboratory reports should be anonymized and will be retrieved by the monitor.

The following parameters need to be tested: aspartate aminotransferase (AST), alanine aminotransferase (ALT), creatinine, erythrocyte sedimentation rate, and a complete blood cell count (including hemoglobin, hematocrit, red blood cell [RBC] count, white blood cell [WBC] count, neutrophils, lymphocytes, monocytes, eosinophils, basophils, and platelet count).

Digital pictures need to be taken as described below and in Appendix 5. Digital pictures will be anonymized and stored on the Sponsor's secure server. Only the study team will have access to the pictures.

The subject may be treated symptomatically until the rash resolves. If the rash is considered to be most likely due to concomitant illness or non-study medication, standard management, including discontinuation of the likely causative agent, should be undertaken, and the continuation of the subject in the study should be discussed with the Sponsor.

Dermatologist fees for evaluating subjects who experience a rash will be reimbursed by the Sponsor.

The following grades are based on the DAIDS Toxicity Grading Scale (DAIDS 2017) with adaptations made by the Sponsor:

Subjects should be informed that they should contact their doctor and visit the clinic immediately (unscheduled visit, day 1 of the rash) when they notice any rash.

Grade 1 Rash

A Grade 1 rash is defined as **erythema**.

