- Assessment of safety blood samples by the local laboratory is required. A copy of the local laboratory report should be anonymized and will be retrieved by the monitor.
- Digital pictures should be taken within 24 hours after the onset of the rash.
- Referral to a dermatologist is required, preferably within 24 hours after the onset of the rash. A copy of the dermatologist's report should be anonymized and will be retrieved by the monitor.
- A biopsy is performed (preferably within 24 hours after the onset of the rash) if advised by the dermatologist. A copy of the biopsy report should be anonymized and will be retrieved by the monitor.
- Cetirizine, levocetirizine, topical corticosteroids, or antipruritic agents may be prescribed.

• The description of the rash should be reported per 'Unscheduled Visit in Case of Rash' in the eCRF (i.e., the initial rash assessment pages).

For close follow-up of the rash, unscheduled visits will also be performed 1 and 7 days after the initial assessment of the rash. At these visits, safety blood samples and digital pictures should be taken. The follow-up rash assessment pages of the eCRF should be completed for all follow-up visits. For these and all subsequent local laboratory blood sample assessments: a copy of the local laboratory reports should be anonymized and will be retrieved by the monitor.

If the rash is unresolved after 7 days:

- And there is an increase in AST/ALT of 1 or 2 times the baseline value OR an increase in AST/ALT of less than 5 times the upper limit of normal (ULN), subjects should be followed weekly with repeated local lab assessments and digital pictures until resolution of the AST/ALT abnormalities.
- And there is no increase in AST/ALT, additional unscheduled visits (including local lab assessments and digital pictures) may be performed at the Investigator's discretion.

Upon resolution/stabilization of the rash, digital pictures should be taken and the final rash assessment pages of the eCRF should be completed.

The subject should be advised to contact the Investigator immediately if the rash fails to resolve (after more than 2 weeks), if there is any worsening of the rash, if any systemic signs or allergic symptoms develop, or if mucosal involvement develops.

In case the rash evolves from a Grade 2 to a Grade 3–4 rash, additional unscheduled visits must be conducted according to the guidelines for Grade 3–4 rash.

Grade 3 or Grade 4 Rash

A Grade 3 rash is defined as:

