- vesiculation, moist desquamation, or ulceration OR
- cutaneous event with one of the following (revised by the Sponsor):
 - elevations in AST/ALT more than $2\times$ baseline value and $\geq 5\times$ ULN
 - fever >38°C or 100°F
 - eosinophils >1000/mm³
 - serum sickness-like reaction

A Grade 4 rash is defined as:

- exfoliative dermatitis OR
- a generalized rash with mucous membrane involvement OR
- erythema multiforme OR
- Stevens-Johnson Syndrome OR
- rash associated with necrosis requiring surgery

- Subjects will **permanently discontinue** the intake of all study drug(s) and be withdrawn from the study with Grade 3 or 4 rash identified. No rechallenge is allowed.
- An unscheduled visit for initial rash evaluation (day 1 of the rash) is required.
- Assessment of safety blood samples by the local laboratory is required on the day of initial
 rash evaluation and the day thereafter (days 1 and 2 of the rash), and as indicated below.
 A copy of the local laboratory report should be anonymized and will be retrieved by the
 monitor.
- Digital pictures should be taken within 24 hours after the onset of the rash and on day 1 of the rash, and as indicated below.
- Referral to a dermatologist is required, preferably within 24 hours after the onset of the rash. A copy of the dermatologist's report should be anonymized and will be retrieved by the monitor.
- A biopsy should be performed within 24 hours after the onset of the rash. A copy of the biopsy report should be anonymized and will be retrieved by the monitor.
- Appropriate management should be undertaken and subjects should be followed until resolution of the rash.
- The description of the rash should be reported per 'Unscheduled Visit in Case of Rash' in the eCRF (i.e., the initial rash assessment pages). The follow-up rash assessment pages of the eCRF should be completed for all follow-up visits.

For close follow-up of the rash, unscheduled visits will be performed as follows:

- Follow-up visits on days 2, 3, and 4 of the rash are required. Additional safety blood samples and digital pictures are to be taken on these days only if the subject's AST/ALT on day 1 and/or day 2 of rash >2× baseline value, and/or ≥5 × ULN and/or in case of rash progression. For these and all subsequent local laboratory blood sample assessments: a copy of the local laboratory report should be anonymized and will be retrieved by the monitor.

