- A follow-up visit on day 6 of the rash is required and additional safety blood samples and digital pictures are to be taken regardless of the day 1/2 AST/ALT levels or rash progression.
- Thereafter, weekly follow-up visits are required (or more frequently at the Investigator's discretion) as long as Grade 3–4 rash is present. Once Grade 3–4 rash has resolved to Grade ≤2, follow-up should be performed according to the instructions for follow-up visits for Grade 1 or Grade 2 rash, respectively.
- As long as the rash remains Grade 3 or 4, additional safety blood samples and digital pictures are required at these weekly follow-up visits only if the subject's AST/ALT on day 6 of rash is still >2× baseline value and/or ≥5 × ULN and/or in case of rash progression, until resolution or stabilization of the AST/ALT elevations.

Upon resolution/stabilization of the rash, digital pictures should be taken and the final rash assessment pages of the eCRF should be completed.

Subjects should be advised to contact the Investigator immediately if they notice any worsening of the rash.

A complete summary of the guidelines for rash management is given in Appendix 5.

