Rash day 4	No Rash follow-up visit required ^c	No Rash follow-up visit required °	Follow-up visit REQUIRED. Assessment of safety blood sample by local laboratory and digital pictures REQUIRED only if on days 1 and/or 2 of rash AST/ALT >2× baseline value, AND/OR 5 × ULN, AND/OR in case of rash progression.

	Grade 1 Rash	Grade 2 Rash	Grade 3 or 4 Rash
Rash day 5	No Rash follow-up visit required °	No Rash follow-up visit required °	Follow-up visit REQUIRED. Assessment of safety blood sample by local laboratory and digital pictures REQUIRED only if on days 1 and/or 2 of rash AST/ALT >2× baseline value, AND/OR 5 × ULN, AND/OR in case of rash progression.
Rash day 6	No Rash follow-up visit required °	No Rash follow-up visit required °	 Follow-up visit REQUIRED. Assessment of safety blood sample by local laboratory REQUIRED. Digital pictures REQUIRED.
Rash day 7	No Rash follow-up visit required ^c	No Rash follow-up visit required ^c	No Rash follow-up visit required
Rash day 8	 Follow-up visit REQUIRED ^c Assessment of safety blood sample by local laboratory REQUIRED. Digital pictures REQUIRED. 	 Follow-up visit REQUIRED ° Assessment of safety blood sample by local laboratory REQUIRED. Digital pictures REQUIRED. 	No Rash follow-up visit required
Further Visits	If rash is unresolved after second follow-up visit, further visits (with local lab assessments and digital pictures) at the Investigator's discretion. c	If rash is unresolved after second follow-up visit: With AST/ALT increase ≤2× baseline value OR AST/ALT increase ≤5 × ULN: ° • Weekly assessment of safety blood sample by local laboratory REQUIRED until resolution of AST/ALT abnormalities. • Weekly digital pictures REQUIRED until resolution of AST/ALT abnormalities. Without AST/ALT increase: further visits at the Investigator's discretion. °	Weekly follow-up visits REQUIRED until resolution of Grade 3–4 rash to Grade ≤2 (further follow-up visits according to Grade 1 or Grade 2 rash instructions) Weekly assessment of safety blood sample by local laboratory and digital pictures REQUIRED as long as Grade 3 or 4 rash is present but only if on day 6 of rash AST/ALT >2× baseline value, AND/OR 5 × ULN, AND/OR in case of rash progression, until resolution of AST/ALT abnormalities.

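### After rash day 6, a non-progressing Grade 3-4 rash with a mild AST/ALT rise has no required weekly blood sample, although an unresolved Grade 2 rash with the same rise does (low severity)

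*Protocol*

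**What the plan says.** The follow-up schedule in Protocol Appendices 4 and 5 applies "in case of a causal relationship between the rash and the study drug".

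**Grade 3 or 4 rash.** Blood is required on rash days 1, 2 and 6, the last whatever the earlier results. From then on a visit is required every week while the rash stays at that grade. Blood at those visits is conditional: "additional safety blood samples and digital pictures are required at these weekly follow-up visits only if the subject's AST/ALT on day 6 of rash" remains above twice baseline and/or at least 5 × ULN, or the rash progresses. The Further Visits row of Appendix 5 has the same condition: weekly blood and pictures are "REQUIRED as long as Grade 3 or 4 rash is present but only if on day 6 of rash AST/ALT" exceeds those limits or the rash progresses.

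**Grade 2 rash unresolved after 7 days.** The Appendix 4 trigger is "an increase in AST/ALT of 1 or 2 times the baseline value OR an increase in AST/ALT of less than 5 times" the ULN. The consequence is that "subjects should be followed weekly with repeated local lab assessments and digital pictures until resolution of the AST/ALT abnormalities". Appendix 5 marks this weekly sample as required. If there is no rise, further visits are left to the investigator.

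**Step-down.** "Once Grade 3–4 rash has resolved to Grade ≤2, follow-up should be performed according to the instructions" for the lower grade.

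**The concern.** A safety schedule would be expected to ask for at least as much laboratory follow-up in a severe drug-related rash as in a moderate one. In one band of AST/ALT values these two rules do the reverse. The Grade 2 rule picks up small rises and follows them to resolution. The Grade 3-4 rule starts only above twice baseline or at 5 × ULN.

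The Grade 3-4 condition also looks back to the day-6 value. Suppose enzymes are mildly raised on day 6 and climb later without visible progression of the rash. No sample required by the rash schedule would then show the climb, whereas the weekly Grade 2 samples would. At stake is timely liver follow-up in a rare subject, not any analysis.

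**Working it through.** The protocol states no figure to reproduce, so the check sets the two rules side by side.

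**Inputs**
- Grade 3-4 weekly blood (Appendices 4 and 5): value > 2 × baseline, or value ≥ 5 × ULN, or rash progression.
- Grade 2 weekly blood (Appendices 4 and 5): an increase, and either the baseline limb (about 1 to 2 times baseline) or the ULN limb (below 5 × ULN).
- Screening limit for AST/ALT (Section 7.2, exclusion 3c): values of 1.25 × ULN or more are excluded.
- Assumed for illustration, not in the documents: ULN 40 U/L; baselines 20, 30 and 40 U/L.

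**Step 1. Where the rules differ.** The Grade 3-4 rule is silent when value ≤ 2 × baseline, value < 5 × ULN and there is no progression. The Grade 2 baseline limb is ambiguous: it could mean a value up to twice baseline, or a rise as large as one to two baselines. That does not matter here. Every value in the band is below 5 × ULN, so the ULN limb is met on either reading. The band is therefore: above baseline, up to 2 × baseline, below 5 × ULN, no progression.

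**Step 2. Examples without progression (ULN 40 U/L)**

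| Baseline | Value | × baseline | × ULN | Grade 2 weekly blood | Grade 3-4 weekly blood |
|---|---|---|---|---|---|
| 30 | 30 | 1.00 | 0.75 | no | no |
| 30 | 45 | 1.50 | 1.13 | yes | **no** |
| 30 | 58 | 1.93 | 1.45 | yes | **no** |
| 30 | 60 | 2.00 | 1.50 | yes | **no** |
| 30 | 63 | 2.10 | 1.58 | yes | yes |
| 40 | 80 | 2.00 | 2.00 | yes | **no** |
| 40 | 84 | 2.10 | 2.10 | yes | yes |

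With no rise neither rule asks for weekly blood. Above twice baseline, or with progression, the Grade 3-4 rule does, and the gap closes.

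**Step 3. How wide the band is.** This depends on what counts as a rise.
- If any increase over baseline counts, the band is baseline to 2 × baseline. At baseline 20 U/L that is above 20 and up to 40 U/L, all within normal limits.
- If the Grade 2 rule's reference to abnormalities means above ULN, the band runs from ULN (or baseline, if higher) to 2 × baseline. It then exists only if baseline > 0.5 × ULN: none at 20 U/L, 41-60 U/L at 30, 41-80 U/L at 40.
- If baseline respects the screening limit, the band ends below 2 × 1.25 = 2.5 × ULN on either reading.

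**Step 4. Can the case occur?** Appendix 4 lists five criteria for Grade 3 (skin breakdown, or a cutaneous event with AST/ALT elevation, fever, eosinophilia or a serum sickness-like reaction) and five for Grade 4. Only one of these ten involves AST/ALT. A blistering, febrile or mucosal rash can therefore be Grade 3-4 with enzymes only mildly raised, and enzymes that were high at onset may have fallen into the band by day 6.

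**The case against.** The best defence is that the triggers were meant to be complementary, with small rises handled under Grade 2 and large ones under Grade 3-4. That explains the upper end of the Grade 2 rule, because a large enough rise turns the rash into Grade 3. It does not explain the lower limit for Grade 3-4, since most routes to those grades involve no enzyme rise.

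Safeguards count for more:
- Section 11.6 requires drug-related AEs to be followed until resolved or stable. Under Section 11.4.1 a laboratory change that is part of a syndrome is recorded as that syndrome, so following a rash with an enzyme rise may itself imply a test.
- Appendix 4 has every rash discussed with the sponsor, and Appendix 5 lets the investigator add assessments.
- Grade 3-4 subjects are withdrawn, and Table 1 asks for the final-visit procedures, including chemistry, on early discontinuation.

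All of this stands and reduces the gap. None of it fixes a weekly sample, and the timing of the discontinuation visit is not tied to the rash.

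Stronger readings that a reader might infer, and that the documents do not support:
- *Grade 3-4 rash is monitored less overall.* It is not. It has denser visits in the first week, a day-6 sample, a biopsy, and weekly visits whatever the enzymes show.
- *A mild rise may simply be left unfollowed.* The general duties above count against that. What is missing is a required interval.
- *Counting rash-schedule samples gives the total blood difference between grades.* It does not, because discontinuation and routine study tests are additional.
- *A rash that is Grade 3 only through eosinophils cannot be stepped down without a count.* That route also needs a cutaneous event, so clearing of the skin ends it. Otherwise the effect is continued weekly visits, which errs on the safe side.

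**Conclusion.** The point holds and is of low severity. While a drug-related rash stays Grade 3-4 without progressing, an AST/ALT value above baseline, up to twice baseline and below 5 × ULN has weaker required laboratory follow-up after day 6 than the same value in an unresolved Grade 2 rash. Both appendices carry the same Grade 3-4 condition, so this is the rule as written and not a slip in one table.

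The size is small. The gap lies in the rash-schedule samples only, ends on step-down to Grade 2, and covers values below 2.5 × ULN if baseline respects the screening limit. Whether values within normal limits belong to the band depends on how a rise is read, which the text leaves open. The U/L examples rest on an assumed ULN.

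The documents give no rate for this event. Section 4.1.2.2 reports only Grade 1 or 2 TEAEs in the first-in-human study, so most likely none of the 27 subjects would be affected. No endpoint, TEAE summary or halt rule changes. It is worth correcting because the correction is cheap, not because the trial is at risk.

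**What to change.** In Appendix 4 (Grade 3 or Grade 4 Rash) and the matching Further Visits cell of Appendix 5, add one sentence. At each weekly Grade 3-4 visit, the local rash panel is required whenever the last sample shows an AST/ALT increase that would trigger the Grade 2 rule, as well as under the present triggers, until the AST/ALT abnormality resolves or stabilises. Using the Grade 2 trigger gives both grades the same definition of a rise, and referring to the last sample removes the dependence on day 6. The rest of the schedule can stay.

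The cost is one sentence in each appendix. The weekly visits are already required, and AST and ALT are already in the local rash panel, so there is no new visit and no new assay. The downside is a few extra local blood draws in a rare subject.

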APPENDIX 5. VISIT SCHEDULE FOR RASH MANAGEMENT FOR ADULT SUBJECTS

This visit schedule summarizes the visits and assessments to be performed in case of rash. At the Investigator's discretion, additional visits and assessments may be performed. For all rashes, please also complete the specific rash assessment pages of the eCRF for all visits. Local laboratory blood sample assessments will be documented/collected as described in the text above.

	Grade 1 Rash	Grade 2 Rash	Grade 3 or 4 Rash
Rash day 1 a	Study drug(s) MAY be CONTINUED. Unscheduled visit for initial rash evaluation REQUIRED. Assessment of safety blood sample by local laboratory REQUIRED. Digital pictures REQUIRED (within 24 h). Referral to dermatologist ONLY IF rash diagnosis uncertain (within 24 h).	 Study drug(s) MUST be permanently DISCONTINUED if the subject has a persistent (i.e., >5 days with no response to treatment) Grade ≥2 b rash considered related to CD388 by the Investigator. Rechallenge is NOT ALLOWED. Unscheduled visit for initial rash evaluation REQUIRED. Assessment of safety blood sample by local laboratory REQUIRED (within 24 h). Referral to dermatologist REQUIRED (within 24 h). Biopsy IF ADVISED by dermatologist (within 24 h). 	 Study drug(s) MUST be permanently DISCONTINUED. Rechallenge is NOT ALLOWED. Unscheduled visit for initial rash evaluation REQUIRED. Assessment of safety blood sample by local laboratory REQUIRED. Digital pictures REQUIRED (within 24 h). Referral to dermatologist REQUIRED (within 24 h). Biopsy REQUIRED (within 24 h).
Rash day 2	 Follow-up visit REQUIRED. Assessment of safety blood sample by local laboratory REQUIRED. Digital pictures REQUIRED. 	 Follow-up visit REQUIRED. Assessment of safety blood sample by local laboratory REQUIRED. Digital pictures REQUIRED. 	 Follow-up visit REQUIRED. Assessment of safety blood sample by local laboratory REQUIRED. Digital pictures REQUIRED.
Rash day 3	No Rash follow-up visit required ^c	No Rash follow-up visit required ^c	Follow-up visit REQUIRED. Assessment of safety blood sample by local laboratory and digital pictures REQUIRED only if on days 1 and/or 2 of rash AST/ALT >2× baseline value, AND/OR 5 × ULN, AND/OR in case of rash progression.
Rash day 4	No Rash follow-up visit required ^c	No Rash follow-up visit required °	Follow-up visit REQUIRED. Assessment of safety blood sample by local laboratory and digital pictures REQUIRED only if on days 1 and/or 2 of rash AST/ALT >2× baseline value, AND/OR 5 × ULN, AND/OR in case of rash progression.

	Grade 1 Rash	Grade 2 Rash	Grade 3 or 4 Rash
Rash day 5	No Rash follow-up visit required °	No Rash follow-up visit required °	Follow-up visit REQUIRED. Assessment of safety blood sample by local laboratory and digital pictures REQUIRED only if on days 1 and/or 2 of rash AST/ALT >2× baseline value, AND/OR 5 × ULN, AND/OR in case of rash progression.
Rash day 6	No Rash follow-up visit required °	No Rash follow-up visit required °	 Follow-up visit REQUIRED. Assessment of safety blood sample by local laboratory REQUIRED. Digital pictures REQUIRED.
Rash day 7	No Rash follow-up visit required ^c	No Rash follow-up visit required ^c	No Rash follow-up visit required
Rash day 8	 Follow-up visit REQUIRED ^c Assessment of safety blood sample by local laboratory REQUIRED. Digital pictures REQUIRED. 	 Follow-up visit REQUIRED ° Assessment of safety blood sample by local laboratory REQUIRED. Digital pictures REQUIRED. 	No Rash follow-up visit required
Further Visits	If rash is unresolved after second follow-up visit, further visits (with local lab assessments and digital pictures) at the Investigator's discretion. c	If rash is unresolved after second follow-up visit: With AST/ALT increase ≤2× baseline value OR AST/ALT increase ≤5 × ULN: ° • Weekly assessment of safety blood sample by local laboratory REQUIRED until resolution of AST/ALT abnormalities. • Weekly digital pictures REQUIRED until resolution of AST/ALT abnormalities. Without AST/ALT increase: further visits at the Investigator's discretion. °	Weekly follow-up visits REQUIRED until resolution of Grade 3–4 rash to Grade ≤2 (further follow-up visits according to Grade 1 or Grade 2 rash instructions) Weekly assessment of safety blood sample by local laboratory and digital pictures REQUIRED as long as Grade 3 or 4 rash is present but only if on day 6 of rash AST/ALT >2× baseline value, AND/OR 5 × ULN, AND/OR in case of rash progression, until resolution of AST/ALT abnormalities.
Upon Rash Resolution/ Stabilization ^d	Complete final rash assessment pages of the eCRF/eSource and take digital pictures.	Complete final rash assessment pages of the eCRF/eSource and take digital pictures.	Complete final rash assessment pages of the eCRF/eSource and take digital pictures.

- a. Note that Day 0 of the rash is the first day of Investigator assessment and not the first day of rash as reported by the subject.
- b. All grades in this list are per the DAIDS Toxicity Grading Scale (DAIDS 2017).
- c. In case rash progresses from a Grade 1 or a Grade 2 to a higher grade, start follow-up schedule for Grade 2, 3, or 4 rash as appropriate.
- d. Stabilization: to be agreed upon in collaboration with the Sponsor

